1. Hypothesis and Specific Aims

Overarching Hypothesis: Insulin signaling is a critical neurobiological substrate of anhedonia in mood disorders

Specific Hypotheses: In individuals with mood disorders, objective and self-reported measures of anhedonia and reward behaviors are associated with alterations in insulin signaling-related molecular, cellular and neural substrates. Considering the role of insulin in the regulation of energy expenditure, we primarily hypothesize that individuals with mood disorders will display decreased willingness to make effort for rewards, relative to healthy controls; and that this abnormality will be associated with:

- a) Molecular: Differential gene and protein expression of the metabolic (i.e. PI3K/Akt) and mitogenic (i.e. Ras/MAP kinase) components of the insulin signaling pathway, as well as with components of reward-related processes (i.e. dopamine receptors and transporter)
- b) Physiology: Reduced peripheral sensitivity to insulin and corresponding metabolic correlates, including increased body mass index and dyslipidemia (i.e. peripheral insulin resistance)
- c) Neural Circuits: Diminished response to insulin in cortico-striatal networks (i.e. brain insulin resistance)

Overarching Aim: To determine the role of insulin signaling on the neurobiological substrates subserving anhedonia within individuals with mood disorders.

Specific Aims:

- a) Molecular: Assessment of components of the insulin cascade, as well as of anhedonia and reward-related processes, using a proteomics and gene expression approach;
- b) Physiology: Measurement of peripheral sensitivity to insulin and metabolic correlates, including body mass index and dyslipidemia;
- c) Neural Circuits: Evaluation of the insulin sensitivity of prefrontal (e.g. prefrontal cortex) and striatal (e.g. nucleus accumbens, ventral tegmental area) networks in the resting-state and during an effort-based decision making test, using acutely administered intranasal insulin and functional magnetic resonance imaging (fMRI);
- d) Behavioral: Measurement of willingness to make effort for rewards, as well as of other components of reward response and anhedonia, using validated behavioral tasks and clinical scales (e.g. Snaith-Hamilton Pleasure Scale SHPS).

2. Background and Rationale

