Genes that were differentially expressed between groups were selected for mediation analyses. Diagnosis by BMI effects on expression of dopamine genes were fully mediated by expression of INSR. Analysis of conditional indirect effects showed interactions between INSR and BMI, indicating significantly stronger indirect effects at higher BMI values. In the hippocampus, we observed that expression of insulin receptor substrate 1 and 2 fully mediated the effects of diagnosis on expression of dopamine genes (Figure 2). All models were significant (e.g. DRD1: $R^2 = 0.31$, $F_{6,385} = 29.519$, p < 0.001). These results suggest that the differential expression of dopamine-related molecules in the postmortem brain of individuals with mental disorders is related to altered expression of insulin signaling genes. We also observed that obesity has region-specific moderating effects on gene expression and co-expression, supporting the hypothesis that metabolic systems are critical mediators of dopaminergic function and providing the rationale for further investigation.

Figure 1 – Mean standardized expression values of insulin and dopamine signaling genes in the dorsolateral prefrontal cortex, according to group (HC vs. MI) and obesity (BMI \geq 30 kg/m²). HC: healthy controls; MI: mental illness; BMI: body mass index.

[figure not shown]
[figure not shown]

Figure 2 – Unstandardized path coefficients for a mediation model in the hippocampus, adjusted for age, gender, race, ethanol and nicotine/cotinine. * p < 0.05; ** p < 0.001.

[name] Research Proposal Project Title: Anhedonia and the insulin pathway: a mechanistic nexus for the mood and metabolic disorders comorbidity

3. Design and Methodology

Study population: We propose to recruit 50 adults between the ages of 18 to 50 years: 25 patients with DSM-5 defined MDD or BDI/II, in a depressive episode, recruited from the Mood Disorder Psychopharmacology Unit, University Health Network, and 25 age- and sex-matched healthy controls recruited through local advertisements in the community.

Inclusion criteria (patients):

- 1. Age 18-50
- 2. DSM-5 defined MDD/BD and a total score ≥20 on the Montgomery-Åsberg Depression Rating Scale (MADRS) and no history of dementia or intellectual disability
- 3. A written, voluntary informed consent prior to study enrollment

Exclusion criteria (patients):

- 1. Use of insulin and/or oral hypoglycemiants, due to its confounding effects

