Screening and Baseline Assessment: Patients and healthy controls will first meet, in-person or virtually, with a staff psychiatrist for a clinical consultation or a research team member, respectively. After obtaining consent and if inclusion criteria are met, a medical comorbidity questionnaire will be administered to screen for concurrent and lifetime medical conditions. Participant's demographic characteristics and current medications, as well as lifetime psychotropic medications received will be recorded. We will also assess dietary intake with the Diet History Questionnaire III (DHQ III); smoking, by questioning number of cigarettes smoked per day, age when smoking started, and quitting date, if applicable, to calculate a smoking pack-year history; physical activity using the International Physical Activity Questionnaire (IPAQ); and alcohol and/or substance abuse. In addition, we will assess demographics, socioeconomic status, medical history, and family psychiatric history; childhood trauma history with the Childhood Trauma Questionnaire (CTQ) will also be assessed. Participants will also be asked to complete an MRI screening questionnaire to ensure that they have no contraindications. The following self-reported measures will be carried out: Perceived Deficits Questionnaire-Depression (PDQ-D), Sheehan Disability Scale (SDS), UCLA life Stress (Episodic), DeJong Gierveld Loneliness Scale, and Pittsburg Sleep Quality Index (PSQI) (Table 1).

When in-person visits are possible, participants will complete a urine drug screen. Female participants will be asked to do blood work to confirm they are not pregnant.

Physiological Assessment: Anthropometric (i.e. BMI, waist-hip ratio) and metabolic measurements (i.e. fasting glucose, fasting insulin, glycated hemoglobin, lipids and HOMA-IR) will be completed at each study visit (1-3). In addition, physical activity and energy expenditure will be measured using an accelerometer. Participants must wear the accelerometer at all times for one week and return it upon Visit 3 for data collection and analysis. Additionally, a heart rate monitor device will be connected to the accelerometer that will monitor heart rate variability over one day of the week that the subjects wear the accelerometer.

Laboratory Assessment:

Routine: the following laboratory tests will be completed:

Triglycerides
Total Cholesterol
Insulin
Glucose
HbA1c
C-Peptide
IGF-1
TSH
Free T4
Free T3
C-Reactive Protein
hCG

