Biomarkers: High sensitivity CRP and TNF α will be measured at both visits (hs-CRP only). Ultrasensitive ELISA will be used to measure high-sensitivity CRP and TNF- α , TNF-RI and TNF-R2 (measured at both visits). For exploratory mechanistic analysis, a 10-plex immunoassay of

inflammatory cytokines will be measured at both visits (e.g. IFN- γ , IL-1 β , IL-2, IL-4, IL-6, IL-8, IL-10, IL-12p70, IL-13). Blood will be collected after a 12 hour fast and centrifuged at 1000g for 15 min at 4°C; plasma will be stored at -80 °C.

Behavioral assessment: These tasks are simple, user-friendly tools that provide an opportunity, when used in conjunction with the most widely used questionnaires, to gain novel insights on reward behaviors in mood disorders.

- a) The primary behavioral measurement will be effort-based decision-making, assessed using the Effort-Expenditure for Rewards Task (EEfRT)³³, which will be done in a fMRI paradigm⁷³, as described below during Visits 2 and 3.
- b) Assessments will include the validated anhedonia scale Snaith-Hamilton Pleasure Scale (SHPS), the mood questionnaires Montgomery-Åsberg Depression Rating Scale (MADRS) and Young Mania Rating Scale (YMRS) during each study visit, and the Bandit Task during the first visit.

Neural Circuits Assessment: A promising tool to study the effect of insulin on CNS is intranasal insulin, which is delivered directly into the brain, without relevant effects on peripheral glucose^{76,77}. A single dose of intranasal insulin has been shown to influence brain activation, increasing regional perfusion and functional connectivity between the hippocampus and the PFC⁷⁸⁻⁸⁰. Acute administration of intranasal in randomized, placebo-controlled, cross-over designs has been previously used to determine regional responses to insulin in the resting-state or during tasks^{78,80}.

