Heart Rate (bpm)	✓	✓	✓		
Waist/hip	✓				
Circumference (cm)					
Physical Activity/	✓	✓	✓		
Energy Expenditure/					
7-Day Accelerometer					
Wear Time Log					
Laboratory Assessme					
Triglycerides	√	√	√		
Total Cholesterol	√	√	√		
Insulin	√	√	√		
Glucose	✓	✓	✓		
HbA1c	✓	✓	✓		
C-Peptide	✓	✓	✓		
IGF-1	✓	✓	✓		
TSH	✓	✓	✓		
Free T4	✓	✓	✓		
Free T3	✓	✓	✓		
C-Reactive Protein	✓	✓	✓		
hCG	✓				
Imaging					
fMRI-EEfRT		✓	✓		
Dimensional Measures					
Clinician Administered					
YMRS	✓	✓	✓		
MADRS	✓	✓	✓		
Bandit Task	✓				
Self-Report					

SHPS	✓	✓	✓	
PDQ-D	✓			
SDS	✓			
UCLA Life Stress	✓			
Interview (Episodic)				
CTQ	✓			
DeJong Gierveld	✓			
Loneliness Scale				
Diet History	✓			
Questionnaire (III)				
IPAQ	✓			
PSQI	✓			
Neurocognitive Tasks				
DSST	√	 	√	
RAVLT	✓	✓	✓	
TMT A/B	✓	✓	✓	

Project Title: Anhedonia and the insulin pathway: a mechanistic nexus for the mood and metabolic disorders comorbidity

Imaging procedures will be started with a safety monitoring for glucose and cardiovascular vital signs. An insulin/placebo spray will be administered intranasally and, within 30 min, fMRI measurement will be performed. Venous blood samples, for determination of plasma glucose and insulin concentrations, will be obtained at the time of the insulin/placebo spray administration and immediately after the scan. The 2 scans for each individuals will be acquired on the same scanner. Subjects will be scanned using a 3.0-Tesla Signa HDx scanner with an 8-channel phased-array receiver coil (GE Healthcare, Milwaukee, Wisconsin) consisting of a structural and functional neuroimaging, comprising:

- Whole-brain 3-D T1-weighted Inversion-Recovery prepared Fast Spoiled Gradient-Echo (IRi. FSPGR) anatomical scan with the following parameters: (TI/TR/TE = 450/8/3 ms, matrix size 256 \times 256, field of view 22 \times 22 cm, slice thickness = 1 mm, and flip angle = 15°)
- Whole-brain, T2*-weighted BOLD echo planar imaging (EPI) during awake resting state with the ii. following parameters: (TR/TE = 2000/30 ms, 3.5 x 3.5 x 3.5 mm voxel size, field of view 24x24 cm, 39 slices, slice thickness 3.5 mm, matrix size 64x64, number of frames = 405, flip angle =
- Three runs of whole-brain, T2*-weighted BOLD EPI series during task-based reward paradigm iii. with the same parameters as in ii.

4. Study Treatment

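### Hypothesis (b) and Aim (b) name dyslipidemia, but only triglycerides and total cholesterol are assayed; without HDL it is only partly measured

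*Combined protocol and SAP*

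**What the plan says.** Section 1 puts dyslipidemia in the physiological hypothesis, "Reduced peripheral sensitivity to insulin and corresponding metabolic correlates, including increased body mass index and dyslipidemia", and again in Specific Aim (b), "Measurement of peripheral sensitivity to insulin and metabolic correlates, including body mass index and dyslipidemia".

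Section 3, Physiological Assessment, lists the metabolic measurements for visits 1 to 3 as "fasting glucose, fasting insulin, glycated hemoglobin, lipids and HOMA-IR". It does not say which lipids. The Laboratory Assessment that follows is introduced by "Routine: the following laboratory tests will be completed" and names twelve tests. Two of them are lipids: "Triglycerides" and "Total Cholesterol". Table 1 repeats the same twelve tests in the same order, with both lipids ticked at V1, V2 and V3.

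The Biomarkers paragraph adds CRP, TNF markers and cytokines, and states the fasting condition: "Blood will be collected after a 12 hour fast". No section plans an HDL, LDL, non-HDL or apolipoprotein assay. Dyslipidemia is not defined anywhere, and Section 6 names no lipid variable for analysis.

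**The concern.** An aim that names dyslipidemia needs assays from which dyslipidemia can be described. Two lipid tests leave HDL and LDL undetermined, and a later analysis plan cannot recover an analyte that was not run. What is at stake is how completely the metabolic part of hypothesis (b) can be answered: any statement about HDL or LDL, or any composite built on them, falls outside the planned data. Total cholesterol is a poor substitute because it sums components that may move in opposite directions.

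**Working it through.** The plan gives no effect size, power or definition for a lipid endpoint, so there is no figure of its own to reproduce. The check has three parts.

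**1. Do the two lists agree?** The Section 3 list has 12 tests, of which 2 are lipids. The Table 1 laboratory rows also have 12 tests, of which 2 are lipids, in the same order. Because both places agree, a row lost in conversion from PDF is an unlikely explanation for the missing HDL.

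**2. What do two assays determine?** Assumption, not in the documents: the usual fasting approximation, total = HDL + LDL + TG/2.2 (mmol/L). With total cholesterol and triglycerides known, one equation links two unknowns. Take total 4.8 and triglycerides 1.6, so that TG/2.2 = 0.73:

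- HDL 1.5: LDL = 4.8 - 1.5 - 0.73 = 2.57; non-HDL = 4.8 - 1.5 = 3.3; TG/HDL = 1.6/1.5 = 1.07.
- HDL 0.9: LDL = 4.8 - 0.9 - 0.73 = 3.17; non-HDL = 4.8 - 0.9 = 3.9; TG/HDL = 1.6/0.9 = 1.78.

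The planned data record these two people identically.

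**3. How far can total cholesterol move?** Same approximation, LDL held constant, all shifts assumed. The net change is -(HDL fall) + (TG rise)/2.2:

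| HDL fall (mmol/L) | TG rise (mmol/L) | Net change in total cholesterol (mmol/L) |
|---|---|---|
| 0.20 | 0.2 | -0.20 + 0.09 = -0.11 |
| 0.05 | 0.2 | -0.05 + 0.09 = +0.04 |
| 0.20 | 0.6 | -0.20 + 0.27 = +0.07 |
| 0.05 | 0.6 | -0.05 + 0.27 = +0.22 |

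The change is zero whenever the triglyceride rise is 2.2 times the HDL fall. Offsetting is therefore possible, but how complete it is depends on the shifts assumed.

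**Illustrative power.** Section 3 plans 25 patients and "25 age- and sex-matched healthy controls recruited through local advertisements in the community". The calculation uses 25 per group, two-sided alpha 0.05, mg/dL units (total = HDL + LDL + TG/5) and assumed SDs. For a triglyceride rise of 40 and an HDL fall of 8:

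- Total cholesterol: net 40/5 - 8 = 0, so power equals alpha, 5%.
- HDL, if assayed (SD 15 to 12): about 47% to 65%.
- Triglycerides, already assayed (SD 80 to 50): about 42% to 81%.

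Over triglyceride rises of 20 to 60 and HDL falls of 4 to 12, the net change in total cholesterol runs from -8 to +8 mg/dL, with power about 5% to 16% (SD 30 to 40). HDL would have about 16% to 94%, and triglycerides about 14% to 99%. Section 6 gives a larger enrollment goal of 150, under which power for any non-zero shift would be higher.

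**The case against.** The strongest reply is that dyslipidemia is not unmeasured. Fasting triglycerides are on both lists at every visit, and a triglyceride difference would be seen directly whatever total cholesterol did. In the illustration above, triglycerides have power comparable with HDL, so adding HDL does not turn a blind study into a sighted one. Dyslipidemia is also one example beside body mass index, while insulin sensitivity itself is covered by fasting glucose, fasting insulin, HOMA-IR, HbA1c and C-peptide. The generic mention of lipids may have been meant as a fuller panel.

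Most of this stands, and it limits the point. It does not remove it: HDL and everything derived from HDL remain unobtainable, and if a fuller panel was meant, both explicit lists need correcting.

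Three stronger readings are tempting and are not supported:

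- A reader might infer that a null result on total cholesterol will be taken as absence of dyslipidemia. No section says dyslipidemia will be judged by total cholesterol.
- A reader might infer that a weak mediator or covariate is being used. Section 6 gives the mediator as insulin signaling and dopamine metabolism, offers obesity and medications as examples of moderators, and gives no role to any lipid.
- A reader might want to pay for HDL by cutting repeat HbA1c and thyroid tests. That is a separate preference. Section 3 places glycated hemoglobin at each visit, and the documents give no assay costs.

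**Conclusion.** The point holds in a limited form. If the plan is followed as written, Aim (b) can report on triglycerides and total cholesterol. It cannot report on low HDL, calculated LDL, non-HDL cholesterol or the triglyceride/HDL ratio. That conclusion follows from the two matching test lists and the cholesterol identity, and does not depend on any assumed effect size.

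The insensitivity of total cholesterol is a possibility and not a demonstrated loss: about -0.11 to +0.22 mmol/L over the assumed range, with LDL unchanged. The direction of the shifts, the approximation and the SDs all come from outside the documents.

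The consequence stays within Aim (b). The primary behavioral measure (EEfRT) and the mediation-based sample size do not depend on a lipid. This is a cheap improvement worth making before sampling, and not a threat to the main question.

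**What to change.** Add HDL cholesterol to the Section 3 laboratory list and to Table 1, run on the fasting blood already drawn, at V1 at minimum. State in advance how dyslipidemia is defined for Aim (b), using triglycerides and HDL, with LDL calculated, and not total cholesterol. Replace the generic reference to lipids under Physiological Assessment with the named analytes, so that the text, the list and the table agree.

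If HDL is not added, reword hypothesis (b) and Aim (b) so that they claim only the lipids actually assayed.

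The cost is one routine analyte per participant at V1 (more if repeated), plus a short edit to Section 3, Table 1 and the analytic plan. No extra visit or blood draw is needed.

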4.1 Treatments Administered

Description of Study Medications

The Investigational Pharmacy Services (IPS, also known as the clinical trials pharmacy) at the University Health Network's (UHN's) Toronto Western Hospital (TWH) will be responsible for all study related preparation, dispensing, and documentation. IPS will be responsible for the following study preparation procedures. All active treatment and placebo will be prepared by an IV certified pharmacy technician, under aseptic conditions, in a sterile room, i.e., centralized intravenous additive services (CIVA) area, and verified by a pharmacist.

Dose preparation for the active and placebo nasal sprays follow the same procedure. This will be conducted upon the receipt of an order from the blinded investigator with regard to the number of nasal spray bottles of Humulin® R insulin or diluent to be prepared the pharmacy.

Each product, whether intranasal Humulin[®] R insulin or diluent, will be prepared under the laminar flow hood one at a time. Using aseptic technique, the protective cap is removed from the vial of Humulin® R insulin or diluent (10 mL/vial, manufactured by Eli Lilly) and the rubber stopper is swabbed with an alcohol swab and allowed to dry. Using an appropriate sterile Luer Lock syringe with an appropriately sized needle attached with the bevel of the needle facing up at a 45 degree angle, the Humulin® R insulin or diluent vial is punctured and 5 mL of insulin or diluent is removed and transferred to a metered dose nasal spray bottle (PharmaSystems, Inc.) provided by the study coordinator overseeing the project herein. The nasal spray bottle is then capped accordingly. In summary, the intranasal solutions are prepared as follows:

• Intranasal Insulin Arm: IPS will obtain commercial supplies of Humulin® R insulin (10 mL/vial, manufactured by Eli Lilly) and aseptically transfer a 5 mL sample into a metered dose nasal spray bottle (PharmaSystems Inc.).

Project Title: Anhedonia and the insulin pathway: a mechanistic nexus for the mood and metabolic disorders comorbidity

Intranasal Placebo Arm: IPS will obtain commercial supplies of Humulin® R insulin's diluent (10 mL/vial, manufactured by Eli Lilly) and aseptically transfer a 5 mL sample into a metered dose nasal spray bottle (PharmaSystems Inc.).

This procedure is repeated until the required number of nasal spray bottles has been prepared. Once completed, the nasal spray bottles are wiped with 70% isopropyl alcohol soaked gauge and removed from the laminar flow hood and appropriately labeled.

Both active and placebo nasal spray bottles are kept separate from each other and a worksheet will be completed to document information, including date of preparation, batch #, expiry date, drug name and strength. The IV certified pharmacy technician who has prepared the dose is responsible for completing the documentation and will be affixing the labels identifying what was prepared. The labels, at a minimum, will contain information regarding the lot #, strength, date of manufacture, expiry date, and storage conditions. All of this will be verified by a pharmacist.

Labeling

All labels will contain product name, volume, protocol number, investigational drug warning, dosage instructions, storage conditions, lot number, expiration date, and the pharmacy name.

Storage

Please refer to the pharmacy manual for information on storage.

Study Medication Administration

This will be a single-dose, randomized, double-blinded, cross-over study involving intranasal insulin/placebo solution.

Designated pharmacy staff will dispense study medication, in a double-blind manner, according to the randomization code specific to each subject and dosing period.

Details regarding intranasal insulin and diluent can be referred to in the pharmacy manual.

The investigator and/or designee will instruct the study participant on how the intranasal insulin/placebo spray should be administered. Each study participant is to receive a single dose of Humulin R 160 U / placebo.

- Given:
 - The nasal spray bottles provide a deliverable volume of 0.1 mL/spray.
 - o Humulin R insulin will be sourced as 100 units/mL in a vials of 10 mL from Eli Lilly.
 - o Diluent will be sourced as 10 mL/vial from Eli Lilly.
- Each spray will offer:
 - o 0.1 mL (i.e., 10 units) of Humulin R insulin
 - o 0.1 mL of diluent (to serve as placebo)
- To obtain a dose Humulin R 160 U / placebo
 - o 16 sprays (0.1 mL/spray) are to be given per dose

- o This works out to 16 sprays split between each nostril such that each nostril receives 8 sprays.
- The sprays will be administered between alternating nostrils.

Given this is a crossover study, the study participants will receive a total of two doses in this study. The time between 2 doses is one week.

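### Do the bottle labels described in section 4.1 break the double blind?

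*Combined protocol and SAP*

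**What the plan says.** All the label text is in section 4.1 of the combined protocol and SAP.

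- **Preparation** (Description of Study Medications). The technician fills the spray bottles under the hood, completes a worksheet that includes drug name and strength, and "will be affixing the labels identifying what was prepared. The labels, at a minimum, will contain information regarding the lot #, strength". Active and placebo bottles are stored apart, and a pharmacist verifies the work.
- **Labeling.** "All labels will contain product name, volume, protocol number, investigational drug warning, dosage instructions, storage conditions, lot number, expiration date, and the pharmacy name".
- **Dispensing** (Study Medication Administration). "Designated pharmacy staff will dispense study medication, in a double-blind manner, according to the randomization code specific to each subject and dosing period".
- **Ordering.** Preparation starts on "an order from the blinded investigator with regard to the number of nasal spray bottles of Humulin" R insulin or diluent.
- **Administration.** The investigator or a designee "will instruct the study participant on how the intranasal insulin/placebo spray should be administered".

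Section 5 sends randomization and masking to the pharmacy manual. The Neural Circuits Assessment text in section 3 does the same for randomization, and section 4.1 does so for details of the two products.

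**The concern.** Insulin has a unit strength ("R insulin will be sourced as 100 units/mL in a vials of 10 mL"), and the protocol gives none for the diluent. The two are drawn from different vials. A true name or a true strength on the bottle would therefore identify the arm, and a manufacturer's lot number might. The label goes onto the metered-dose bottle itself. No over-label or relabelling step is described, and the Labeling list includes dosage instructions, which are meant for whoever uses the spray. The order from the blinded investigator can also be read as an order by product.

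The stakes would be real. Insulin against diluent is the trial's only randomized comparison. Effort choices on the EEfRT are made after the spray at visits 2 and 3. The self-reported SHPS and the clinician-rated MADRS and YMRS are collected at the same visits. All are open to expectancy, and no analysis can restore a lost blind.

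**Working it through.** No sample size, error rate or effect estimate is involved, so there is nothing to calculate. The check sets the passages side by side and asks what each one establishes.

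1. **Does a label show the true contents?** Yes, at preparation. The person who fills the bottles labels them at that point, next to the worksheet and the pharmacist's check. Staff handling both products have to know which is which.

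2. **Is strength required on the bottle that leaves the pharmacy?** This is not stated. Strength is in the preparation paragraph only. The general list in the Labeling paragraph has product name and lot number but not strength. A bottle that shows both name and strength to the participant comes from joining two lists and adding a location that neither gives.

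3. **Must the product name reveal the arm?** No. In its administration text section 4.1 names the product in combined form, as in "will instruct the study participant on how the intranasal insulin/placebo spray should be administered". A label with a combined name satisfies the Labeling rule and is masked. It is also the reading that agrees with double-blind dispensing.

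4. **Must the lot number reveal the arm?** This is not established. The bottles are prepared in the pharmacy and given a batch number on the worksheet. The protocol does not say whether the lot on the label is the manufacturer's or the pharmacy's, or that blinded staff could decode it.

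5. **Does the order unblind the investigator?** No. It concerns how many bottles to prepare. Which bottle a subject receives in which period follows from the randomization code applied at dispensing. Knowing the stock quantities does not disclose that.

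6. **Does the label rule contradict the masking procedure?** That cannot be shown. The procedure is in a manual outside these documents, and a protocol that delegates masking would be expected to say little about it.

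7. **How many people could be affected?** Each participant receives one dose of each product, so identifying either bottle identifies the other. If every dispensed bottle carried an open label and everyone read it, the count would be 50 of 50. That is a ceiling resting on a premise the text does not state. The protocol also does not say that participants hold the bottle, and Table 1 does not place the SHPS, MADRS or YMRS before or after the spray.

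**The case for a change.** The strongest reply is that the protocol hands storage, accountability, disposition and masking to the pharmacy manual by name, but writes out the labelling rule itself. A manual with masked labels would then sit awkwardly beside a protocol that says labels identify the contents and makes no exception to the product-name rule. The worksheet already keeps identity traceable, so an open bottle label is not needed for that purpose. A technician working from the label sentences alone could print open labels and have them reach the clinic.

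Part of this stands. The label sentences are not explicitly reconciled with the dispensing sentence, and the order is loosely worded. But staff do not work from those sentences alone. The same section requires double-blind dispensing by a code for each subject and period, and sending out a bottle marked as insulin would breach that requirement. A pharmacy that follows the whole section has to mask what it dispenses. The objection shows incomplete drafting. It does not show an instruction that defeats the blind.

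**Conclusion.** The concern does not call for a change. The protocol omits one detail, the form of the label on the dispensed bottle, and leaves masking to the pharmacy manual. Read as a whole, section 4.1 keeps the blind, and an investigational pharmacy running a double-blind study would supply a masked dispensing label in any case. Writing this into the protocol would be an editorial clarification and would not alter the treatment given, the data collected or the conclusions.

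The size of any effect cannot be derived from the documents. The figure of 50 of 50 is a worst case, not an expectation. The comparisons of patients with controls on measures taken at baseline do not depend on this blind at all.

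The conclusion rests on two assumptions: that the pharmacy manual sets out masking, as section 5 says, and that staff apply the double-blind dispensing rule as written. If the manual turned out to require open labels on dispensed bottles, the point would have to be reopened.
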